Date: September 1, 2021

Title: Comparison Effects Of Blue Prescription Program, Home Exercise Program And Supervised Exercise Approaches On Type 2 Diabetic Women.

Identifiers: NCT05479435

STUDY PROTOCOL

Participants: Individuals diagnosed with Type 2 Diabetes were recruited from Balikesir Provincial Health Directorate, Edremit District Health Directorate Healthy Life Center. They were 60 people who were assigned to the groups by using a randomization program.

Inclusion Criteria:

Age between 25-65 years.

Diagnosis of Type 2 Diabetes for at least 5 years.

HbA1c value > 6.5% or fasting blood glucose > 126 mg/dL.

Ability to walk independently.

Voluntary participation in the research.

Exclusion Criteria:

Type 1 Diabetes Mellitus.

Use of insulin.

Orthopedic or neurological conditions hindering exercise.

Cardiovascular, pulmonary, or systemic diseases contraindicating exercise.

Recruitment Details: The study commenced on September 1, 2021, at Balikesir Provincial Health Directorate, Edremit District, Health Directorate's Healthy Life Center in Balikesir, Turkey.

Evaluated Parameters:

Glycosylated Hemoglobin Change: Hemoglobin A1c is a blood test used to measure the effectiveness of treatment in diabetes, and sometimes to diagnose diabetes. The generally accepted reference range for Hemoglobin A1c (HbA1c) is between 4% and 6%.

Physical Activity Level Change: Assessed via International Physical Activity Questionnaire-short form (IPAQ) to evaluate weekly physical activity levels. The questionnaire provides information about the time spent by the individual in light, moderate, and vigorous activities and sitting in the last 7 days. The MET-min / week score is obtained by multiplying the MET value (metabolic equivalent) by days and minutes for each activity level. Physical activity levels are classified as: Physically inactive (<600 MET-min / week),

Low physical activity (600-3000 MET-min / week), and

Adequate physical activity (> 3000 MET-min / week).

A higher score is associated with a higher physical activity level.

Functional Capacity Change with Timed Up And Go Test: The participant will sit on a chair without armrests, stand up with the command to start, walk 3 meters towards the designated point, turn around and walk to the starting point again and sit. The test is repeated 3 times and the average is taken. The time will be recorded in seconds. As time increases, the risk of falling increases.

Functional Capacity Change with 6-minute Walking Test: It will be performed in a 30 meter long corridor or in an open area. The participant will be asked to walk without running at the highest speed for 6 minutes. Before and during the march, the participant will be verbally encouraged and motivated. How many meters they walked will be recorded as a result of the test. Six-minute walk test results can be interpreted as follows:

Normal: more than 500 meters

Light restriction: 400 to 500 meters

Moderate restriction: 300 to 400 meters

Severe restriction: between 200 - 300 meters

Serious restriction: less than 200 meters.

Fasting Plasma Glucose: Measures blood glucose levels after fasting for 8-12 hours. Assessed at baseline and 12 weeks. The unit of measurement is mg/dL, the reference range is 70-110 mg/dL.

High Density Lipoprotein (HDL): It takes part in the transport of cholesterol from tissues and vessels to the liver and in the synthesis of vitamin D. The unit of measurement is mg/dL, the reference range is 30-96 mg/dL.

Low Density Lipoprotein (LDL): It provides the transport of cholesterol synthesized in the liver to the tissues and blood vessels. The unit of measurement is mg/dL, the reference range is 0- 130 mg/dL.

Total Cholesterol: Total cholesterol is a value that shows the total amount of cholesterol in the blood. In addition to LDL and HDL, triglyceride levels are also used to calculate total cholesterol. The unit of measurement is mg/dL, the reference range is 70-200 mg/dL.

Triglyceride: It is a storage nutrient molecule formed by the combination of fatty acids and glycerol molecules, which form the structure of fats in foods. The unit of measurement is mg/dL, the reference range is 0-250 mg/dL.

C-reactive Protein: It is a protein produced in the liver. It is a protein that is produced by cells and secreted into the blood when the body reacts to conditions such as infection, tumor, trauma, and undertakes various biochemical tasks. The unit of measurement is mg/dL, the reference range is 0-0.5 mg/dL.

Systolic and Diastolic Blood Pressure: Measured with a sphygmomanometer. Baseline and 12 weeks.

Heart Rate: Measured in beats per minute (bpm). Baseline and 12 weeks.

Body Composition Analysis: Assessed using Bioelectrical Impedance Analysis (BIA) and Skinfold Analysis. Baseline and 12 weeks.

Flexibility Measurements: Evaluated using Fingertip-to-floor Distance Measure and Trunk Lateral Flexion Measure. Baseline and 12 weeks.

Quality of Life, Depression, and Contentment: Assessed using various scales (DQOL, Beck Depression Scale, DTSQ). Baseline and 12 weeks.

Anthropometric Measurements: Height, weight, neck circumference, waist circumference, hip circumference, and Body Mass Index (BMI). Baseline and 12 weeks.

Experimental Groups:

Blue Prescription Group: Participants receive a personalized exercise program, motivational support, and follow-up by a physiotherapist. Communication is maintained throughout the study.

Video-Based Home Exercise Group: Participants receive exercise videos, perform exercises independently, and are monitored via phone calls. Assessments are conducted at 12 weeks.

Supervised Exercise Group: Participants engage in supervised exercise sessions led by a physiotherapist. Training and assessments are conducted at 12 weeks.

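### Does the missing sex criterion in the eligibility list mean the trial could study a population other than the women named in its title?

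*Protocol*

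**What the plan says.** The protocol and the SAP carry the same title, which names the population: "Supervised Exercise Approaches On Type 2 Diabetic Women".

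The body of the protocol does not repeat the restriction. Its Participants paragraph opens with "Individuals diagnosed with Type 2 Diabetes were recruited from Balikesir Provincial Health Directorate", and the next sentence gives the sample in equally neutral terms, as 60 people allocated by a randomisation program. The Inclusion Criteria are five: an age range ("Age between 25-65 years"), a minimum time since diagnosis, a glycaemic threshold, unaided walking and willingness to take part. The four Exclusion Criteria cover type 1 diabetes, insulin treatment, orthopaedic or neurological limits on exercise, and other diseases that make exercise unsafe. None of the nine items refers to sex. Below its title, the SAP does not mention sex as a covariate, a stratification factor or part of an analysis-population definition.

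**The concern.** Site staff screen against the eligibility list, and a reader uses that list to judge whether a participant was properly enrolled. A restriction that appears only in a title is easy to overlook and awkward to audit. Read without the title, the list makes a man eligible if he meets the other criteria.

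If men had been enrolled, two things would be at stake.

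- **The question answered.** The conclusion is framed for women, and only part of the sample would inform it.
- **Precision.** Several outcomes would be expected to differ by sex: HDL, body composition, and neck, waist and hip circumference. The protocol mentions no stratified randomisation. The SAP names ANCOVA without listing covariates, and its Kruskal-Wallis and Mann-Whitney route cannot adjust for one. Nothing in the written plan would deal with a chance sex imbalance between arms.

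**Working it through.** The documents give no figure on sex to reproduce, so the check is mainly a reading of the text. The arithmetic below only shows what the size would depend on.

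**Step 1: where sex appears.**

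| Place | Refers to sex? |
|---|---|
| Protocol title | Yes, women |
| SAP title | Yes, women |
| Participants paragraph | No; neutral nouns |
| Inclusion Criteria | 0 of 5 |
| Exclusion Criteria | 0 of 4 |
| Experimental Groups | No; neutral nouns |
| SAP text below its title | No |

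The two titles agree with each other. No other place says that men are eligible, and none describes a mixed sample.

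**Step 2: contradiction or omission?** A contradiction would need one place to say women only and another to say both sexes. The neutral nouns in the Participants paragraph are true of a group of women as well as of a mixed group. The same holds for the SAP: a single-sex trial has no use for a sex covariate, so its absence fits the title. It becomes a second defect only if one first assumes that men took part. What remains is a restriction stated in the title and not carried into the list.

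**Step 3: what the size depends on.** Let m be the proportion of men among the 60. The number of women is 60(1 − m). The standard error of a women-only contrast, relative to one based on 60 women with the same allocation, is sqrt(60 / [60(1 − m)]) = sqrt(1 / (1 − m)).

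| m | Women | Ratio |
|---|---|---|
| 0 (as the titles state) | 60 | sqrt(60/60) = 1.00 |
| 0.30 (assumed) | 42 | sqrt(60/42) = 1.20 |
| 0.50 (assumed) | 30 | sqrt(60/30) = 1.41 |

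The ratio is a function of m and nothing else. The documents give no value for m other than the zero implied by the titles, so the last two rows restate an assumption and measure nothing about this trial.

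**Step 4: chance imbalance, on the same assumption.** Take 20 per arm (equal allocation is also an assumption, since the protocol gives no arm sizes), unstratified randomisation, and 18 or 30 men in total. The number of men per arm then follows a hypergeometric distribution. A given pair of arms differs by at least 4 men with probability 0.23 (18 men) or 0.27 (30 men). At least one of the three pairs does so with probability 0.44 or 0.50. With no men the probability is zero.

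**The case for a change.** The strongest case for acting is that eligibility criteria, not titles, govern enrolment, and that the repair costs one line. Steps 3 and 4 also show that if a third or a half of the sample were men, the loss of precision and the chance of imbalance would be worth planning for, and the SAP as written would not do so.

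Part of this stands. The list is incomplete as a screening document, and the gap is not a redaction or a conversion fault: both lists read as whole. A tidier protocol would have repeated the restriction.

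The rest is weaker, for three reasons.

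- The Participants paragraph is in the past tense, as though recruitment was over when it was written. In that case, a sex criterion added now would alter no enrolment and no data.
- The precision argument holds only if men were enrolled, and there is no sign of that. Even then, chance imbalance under randomisation is not a systematic bias. The paired within-group comparisons remove stable differences between people, including sex. If the unnamed ANCOVA covariate is the baseline value, which the SAP does not say, much of the stable sex difference would be absorbed there too. That last point does not extend to the Kruskal-Wallis route.
- A sex covariate added as a precaution would have nothing to estimate in an all-female sample.

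**Conclusion.** No change to the plan follows. This is a gap in wording that the title of each document already fills. An analyst who follows the plan in the population it names gets the same estimates, tests and conclusions with or without a sex line in the Inclusion Criteria, so the size of the effect is nil (ratio 1.00).

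This rests on one assumption: that those enrolled were women, as both titles say. The documents neither confirm it with a count nor give any reason to doubt it. Reporting the sex of the 60 participants in the baseline table would settle the matter, and that is a reporting step. Only if the table showed men would the title and population statement need correcting and the handling of sex in the ANCOVA become a live question. Until then, no numerical harm can be claimed.

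### The 6-minute walk calls for verbal encouragement without fixing its wording or timing and describes no masking of the tester, so urging could differ by arm at 12 weeks

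*Protocol*

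**What the plan says.** The protocol's entry for the 6-minute walking test, under Evaluated Parameters, makes the test one of maximal effort: "The participant will be asked to walk without running at the highest speed for 6 minutes". The outcome is distance: "How many meters they walked will be recorded as a result of the test". Between these two sentences stands the rule at issue: "Before and during the march, the participant will be verbally encouraged and motivated". The entry gives course length, duration and bands for interpreting the result. It gives no phrases, no times at which they are spoken and no limit on them, and it does not say who conducts the test. The setting is also left open: "It will be performed in a 30 meter long corridor or in an open area".

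Under Experimental Groups, contact with a physiotherapist differs by arm:

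- Blue Prescription: "Participants receive a personalized exercise program, motivational support, and follow-up by a physiotherapist".
- Supervised Exercise: "Participants engage in supervised exercise sessions led by a physiotherapist".
- Video-Based Home Exercise: "Participants receive exercise videos, perform exercises independently, and are monitored via phone calls".

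Neither document mentions masking of assessors or assessors separate from those who treat. The SAP compares groups by ANCOVA with Tukey post hoc tests, or by Kruskal-Wallis with Mann-Whitney tests if the data are not normally distributed. It has no term or step for the assessor.

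**The concern.** Distance in a maximal walk depends partly on how hard the participant tries, and the protocol tells staff to act on that effort without saying how much or in what way. If the person running the 12-week walk knows the participant or the arm, the urging may be stronger for some arms than for others. The extra metres would then be counted as an effect of the exercise programme.

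Randomisation balances the participants at entry, but it does not control what the tester does twelve weeks later. Adjusting for the baseline walk does not help either, because the shift arises at follow-up. Even if urging is unrelated to arm, variation from one test to the next adds noise to the change in distance. If it changes systematically between visits, it also enters the within-group paired comparisons.

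**Working it through.** **Stated figures.** The documents give no SD, effect size, power or sample-size calculation for the walk, so there is nothing to reproduce. The calculation below illustrates the size of the risk and does not estimate what happened in this trial.

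**Inputs from the documents.** Total sample: "They were 60 people who were assigned to the groups by using a randomization program". There are three arms. The significance level is 0.05. The between-group test for normally distributed data is ANCOVA; the SAP does not name the covariate.

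**Assumed inputs.**

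- Equal allocation: 60 / 3 = 20 per arm (no ratio is stated).
- The walk is done at baseline and 12 weeks. The walk entry does not list visits, but its title speaks of change, and other outcomes give these two times.
- The baseline walk is the ANCOVA covariate, with correlation *r* between visits.
- SD of distance 80 m and *r* = 0.7, varied over 70-90 m and 0.7-0.8.
- No true difference between arms.
- Encouragement adds *b* metres in one arm only, at 12 weeks. The size of *b* drives the result, and nothing in the documents indicates its value.

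**Formula.** With one of three arms shifted by *b*, that arm lies 2*b*/3 above the overall mean and the other two lie *b*/3 below it. The sum of squares is (2*b*/3)² + 2(*b*/3)² = (2/3)*b*². The residual variance after baseline adjustment is SD²(1 − *r*²). The noncentrality is therefore

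λ = 20 × (2/3) × *b*² / [SD² (1 − *r*²)],

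and the chance of a significant result is the probability that a noncentral F with 2 and 56 df exceeds its 5% critical value, 3.16.

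**Base case (SD 80 m, *r* = 0.7).** The residual variance is 6400 × 0.51 = 3264.

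| *b* (m) | λ | False-positive rate |
|---|---|---|
| 0 | 0 | 5% |
| 10 | 1333 / 3264 = 0.41 | 8.0% |
| 20 | 5333 / 3264 = 1.63 | 18.3% |
| 30 | 12000 / 3264 = 3.68 | 36.8% |

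**Sensitivity at *b* = 20 m.**

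| SD (m) | *r* = 0.7 | *r* = 0.8 |
|---|---|---|
| 70 | 22.8% | 30.9% |
| 80 | 18.3% | 24.4% |
| 90 | 15.3% | 20.0% |

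The range is 15-31%.

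**Check without a covariate.** Because the SAP names no covariate, the same three-arm test was run unadjusted, with 2 and 57 df. At *b* = 20 m it gives 34%, 17% and 11% for SDs of 40, 60 and 80 m. The inflation does not depend on the ANCOVA assumption. Its size depends on the ratio of the shift to the residual SD.

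**The case against.** The strongest reply is that the encouragement rule applies to every participant, with no distinction by arm. Encouragement given alike raises all arms alike and leaves the comparison unbiased. That is correct, and it means that encouragement as such is not the fault. What remains is that nothing in the plan makes it alike, or would let a reader confirm that it was.

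A second reply is that this is a very short protocol, so the absence of a script or of masking may be brevity. That also stands in part. A reader might infer that testers were unmasked, or that they chose their own words and amount of urging. The documents do not say so: they do not identify the tester, and they are silent on masking. The supportable statement is that no masking and no script are described. Brevity does not fully answer the point, because the plan actively calls for an influence on effort.

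A reader might also infer that, because Blue Prescription includes motivational support, the test itself delivers part of the intervention under comparison. That rests on a shared word. Motivational support there belongs to a programme with a personalised exercise plan and physiotherapist follow-up; urging during a six-minute walk is a different thing. The arm descriptions matter here only because they show that contact with physiotherapists is uneven.

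Finally, the percentages depend on an assumed shift. That is so, and they should be read only as showing what a shift of a given size would do.

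**Conclusion.** The point holds as a risk of bias in one outcome. The plan instructs encouragement in an effort-dependent test, standardises neither its content nor its timing, and describes no masking, while two of the three arms involve physiotherapist delivery or follow-up. Urging could therefore differ by arm at 12 weeks, and the planned analysis could not separate that from a treatment effect. The documents do not show that it did differ.

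On the stated assumptions, a 20 m difference in one arm would raise the three-arm false-positive rate from 5% to about 18%. A shift near zero would do no harm.

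The scope is limited. The walk is one of many outcomes and no primary outcome is named. Laboratory measures such as HbA1c are not affected by this mechanism. The change is worth making because it is cheap, but the point does not call the trial as a whole into question.

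**What to change.** Replace the encouragement sentence in the walk entry with a fixed script: the same short phrases, spoken at the same minute marks, in every arm and at both visits, with no other encouragement before or during the walk. This costs a one-page script and a short briefing, with no extra visits.

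A script limits tester influence but does not fully remove it, because tone and emphasis can still vary. Where existing staff allow, the walk should therefore be run by someone who does not treat that participant, and preferably by someone who does not know the arm. That costs some scheduling effort and may not always be feasible at a single centre.

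If the data are already collected, the script cannot be applied in retrospect. The report should then state who tested whom, whether they knew the arm and how encouragement was given, and any difference between arms in walk distance should carry that caveat.

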Date: September 1, 2021

Title: Comparison Effects Of Blue Prescription Program, Home Exercise Program And Supervised Exercise Approaches On Type 2 Diabetic Women.

Identifiers: NCT05479435

Statistical Analysis Plan

SPSS 22.0 for MacBook was utilized to analyze the data. The Shapiro-Wilk test was employed to assess whether the data exhibited a normal distribution. Mean, standard deviation, median, and frequency were provided for quantitative data and compared using ANOVA test. Chi-square test was applied for qualitative data analysis. ANCOVA test was utilized for intergroup comparisons of normally distributed data, and Tukey test was used for post hoc analyses. For intra-group comparisons, data were analyzed with paired t-test. Intergroup comparisons of non-normally distributed data were conducted using the Kruskal-Wallis test, and intragroup comparisons were performed with the Wilcoxon signed-rank test. Mann-Whitney U test was employed for pairwise comparisons. The significance level was set at $p \leq 0.05$

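### The SAP names no ANCOVA covariate and does not tie the Tukey test to the ANCOVA model; run literally on raw arm means, the pairwise comparisons would drop the adjustment

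*SAP*

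**What the plan says.** The between-group analysis of normally distributed outcomes is one sentence in the SAP, under Statistical Analysis Plan: "ANCOVA test was utilized for intergroup comparisons of normally distributed data, and Tukey test was used for post hoc analyses". The SAP does not name the covariate, does not say whether the dependent variable is the 12-week value or the change, and does not say whether Tukey is applied to raw means, changes or covariate-adjusted means. ANOVA appears in a separate sentence, attached to the descriptive summaries. Non-normal outcomes go to rank tests and are outside this point.

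The protocol supplies the setting. Under Participants: "They were 60 people who were assigned to the groups by using a randomization program". Experimental Groups describes three active arms. Under Evaluated Parameters, fasting glucose is "Assessed at baseline and 12 weeks", and several other outcomes carry the same two time points. HbA1c, physical activity and the two functional capacity tests are labelled as changes, which implies a baseline measurement.

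**The concern.** The trial asks which of three programmes works better. An overall ANCOVA test can say only that the arms are not all alike; the pairwise comparisons name the better programme. A Tukey test named without qualification is the studentized-range comparison of group means, using the ordinary within-group variance. An analyst who follows the words literally would adjust the overall test and leave the pairwise tests unadjusted.

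Two things are then at stake. First, chance baseline imbalance passes into the pairwise differences, and the variance that baseline explains stays in the error term, so power falls. Second, the two steps can disagree: a significant ANCOVA may be followed by no significant pair, leaving the main question unanswered.

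**Working it through.** The plan has no power calculation to reproduce; 60 is given without inputs. The check is therefore what each reading of the Tukey step would deliver.

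**Inputs from the documents.** 60 participants (protocol, Participants); three arms (protocol, Experimental Groups); significance level 0.05 (SAP).

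**Assumptions.** 20 per arm (the allocation ratio is not stated), two-sided tests, normal data, equal variances, common slope and no dropout. The true difference for the pair of interest is 0.8 SD. The correlation r between baseline and 12 weeks runs from 0 to 0.8. The documents give neither r nor an effect size.

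**Standard error of a pairwise difference, in SD units, n = 20.**
- Raw 12-week means: √(2/n) = √0.1 = 0.316 at every r.
- Adjusted means: about √(2(1 − r²)/n) = 0.316, 0.302, 0.274, 0.226, 0.190 at r = 0, 0.3, 0.5, 0.7, 0.8.
- Change scores: √(2 × 2(1 − r)/n) = 0.447, 0.374, 0.316, 0.245, 0.200.

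**Hand check of power.** The Tukey critical value is q = 3.403 (3 means, 57 df) for raw means and 3.405 (56 df) for adjusted means; dividing by √2 gives about 2.41. A raw difference is significant beyond 2.406 × 0.316 = 0.761 SD. With a true 0.8 SD, power is about Φ((0.8 − 0.761)/0.316) = Φ(0.12) = 0.55. For adjusted means at r = 0.7 the threshold is 2.408 × 0.226 = 0.544 SD, and power is about Φ(0.256/0.226) = Φ(1.13) = 0.87.

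**Simulation.** 20,000 trials per setting, so the Monte Carlo standard error of each proportion is at most √(0.25/20,000) = 0.35 points. Power is for the 0.8 SD pair, with arm means 0, 0.4 and 0.8 SD:

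| r | Raw 12-week means | Adjusted means | Change scores |
|---|---|---|---|
| 0 | 55% | 54% | 28% |
| 0.3 | 55% | 59% | 40% |
| 0.5 | 55% | 69% | 56% |
| 0.7 | 56% | 86% | 80% |
| 0.8 | 55% | 96% | 94% |

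With arm means 0, 0 and 0.8 SD, power for an affected pair agrees within about one point.

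**Disagreement.** With one arm differing (0, 0, 0.8), the share of significant ANCOVAs with no significant raw Tukey pair is:
- r = 0: 0.023/0.712 = 3%
- r = 0.3: 0.071/0.756 = 9%
- r = 0.5: 0.148/0.837 = 18%
- r = 0.7: 0.247/0.951 = 26%
- r = 0.8: 0.280/0.992 = 28%

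Repeat runs move these by up to about one point. With Tukey-Kramer on adjusted means the share is 3% or less throughout (for example 0.021/0.712 = 2.9% at r = 0 and 0.008/0.951 = 0.8% at r = 0.7). The raw-mean share depends on the pattern of means: with 0, 0.4 and 0.8 SD it is 0.162/0.716 = 23% at r = 0.5 and 0.299/0.873 = 34% at r = 0.7. The reverse conflict, a raw pair significant without a significant ANCOVA, occurs in at most 3.5% of all trials in these two patterns.

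**False positives.** With no true differences, family-wise error is 4.8% to 5.4% for raw Tukey and 4.8% to 5.2% for Tukey-Kramer on adjusted means.

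**The case against.** A reader might infer that the plan runs a baseline-adjusted ANCOVA and then tests unadjusted means. The SAP says neither. It names no covariate, and it mentions Tukey in the same sentence as the ANCOVA, as its follow-up. A Tukey-type adjustment of covariate-adjusted means is a valid procedure, and on that reading none of the losses arises. This objection stands: the point is conditional on how the sentence is carried out. That baseline is the covariate is likewise an inference, though a natural one, because an ANCOVA needs a covariate and outcomes are measured at baseline.

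The change labels in the protocol suggest a third reading, Tukey on change scores. That recovers most of the loss at r = 0.7 and 0.8, but gives about the same power as raw means at r = 0.5 and less below that.

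The loss also depends on r. At r = 0 there is none, and at r = 0.3 it is about 4 points, so a large loss cannot be asserted for every outcome.

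Finally, a reader might suspect inflated false positives. The simulation does not support that.

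What the objection does not remove is that the text admits three pairwise analyses that can give different answers, and that the literal one is never materially better than adjusted contrasts.

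**Conclusion.** The point holds as a conditional one. The SAP does not name the ANCOVA covariate or link the Tukey comparisons to the ANCOVA model. If Tukey is run on raw 12-week means, the loss in power for a 0.8 SD pair is nil at r = 0 and about 4, 14, 30 and 40 percentage points at r = 0.3, 0.5, 0.7 and 0.8. The risk of a significant ANCOVA with no significant pair rises with r in the same way. These figures rest on 20 per arm, no dropout, normal data with equal variances, and an assumed effect size and range of r.

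The documents do not support the stronger statement that the plan does discard the adjustment. Type I error is not threatened, and if adjusted means were always intended the change only records that. It is an improvement available at no cost, for normally distributed outcomes only.

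**What to change.** Replace the Tukey wording in the SAP with: 'Pairwise comparisons are contrasts of the baseline-adjusted 12-week means from the ANCOVA model (arm plus the baseline value of that outcome), with Tukey-Kramer (or Sidak/Bonferroni) adjusted p-values and matching simultaneous 95% confidence intervals.' One of the three adjustments should be chosen and named.

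This also settles the choice between 12-week value and change, because with the baseline value in the model both give the same adjusted contrasts. The cost is one sentence. No new data are needed where baseline is already measured. The protocol gives no time points for the lipids and C-reactive protein, so the wording assumes that these too are measured at baseline and 12 weeks.

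### Outcomes that fail the normality test go to rank tests with no baseline adjustment; a rank ANCOVA would keep it using data already planned

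*SAP*

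**What the plan says.** The rule is set out in the single paragraph of the Statistical Analysis Plan. The switch is a normality test: "The Shapiro-Wilk test was employed to assess whether the data exhibited a normal distribution". If it is passed, "ANCOVA test was utilized for intergroup comparisons of normally distributed data, and Tukey test was used for post hoc analyses". If it is failed, "Intergroup comparisons of non-normally distributed data were conducted using the Kruskal-Wallis test", and "Mann-Whitney U test was employed for pairwise comparisons".

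The SAP leaves four things open:

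- which covariate enters the ANCOVA;
- whether Kruskal-Wallis is run on 12-week values or on changes;
- whether Shapiro-Wilk is applied once per outcome or separately by arm and visit;
- whether the Mann-Whitney tests wait for a significant Kruskal-Wallis result or carry any correction.

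Baseline values are part of the plan. For the non-normal outcomes, "intragroup comparisons were performed with the Wilcoxon signed-rank test", which is impossible without pre/post pairs. The Protocol (Evaluated Parameters) states both visits for fasting glucose, blood pressure, body composition and the questionnaire scales, among others. It titles HbA1c, physical activity, Timed Up and Go and the 6-minute walk as changes.

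On size, the Protocol (Participants) says "They were 60 people who were assigned to the groups by using a randomization program". There are three arms. No allocation ratio, effect size, SD or correlation is given.

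**The concern.** The question in the trial's title is the comparison between programmes. For any outcome that fails the normality test, that comparison is made without a covariate, while the within-group comparison of the same outcome does use baseline. If 12-week values are ranked, baseline is discarded. If changes are ranked, it enters with a weight of exactly 1, which is inefficient unless the correlation is high.

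Leaving raw-scale ANCOVA for a badly skewed outcome is reasonable. The weakness is what replaces it. With 60 people in three arms, power between programmes is already limited, and the plan gives some away. A normality test also decides whether an outcome can be adjusted at all, so outcomes within one trial may answer differently adjusted questions.

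**Working it through.** **Inputs.** From the documents: N = 60, three arms, significance at 0.05. Assumed, because the documents are silent: 20 per arm, no dropout, effects of 0/0.35/0.7 SD across the arms on the latent scale, and baseline to 12-week correlation ρ from 0.3 to 0.8. The plan has no power figure to reproduce.

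**Large-sample formulas.** With outcome variance σ² at each visit, the variance governing the arm comparison is σ² for 12-week values, 2σ²(1 − ρ) for changes and σ²(1 − ρ²) for ANCOVA. Hence:

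- ANCOVA relative to 12-week values: 1 − ρ²
- ANCOVA relative to changes: (1 − ρ²) / [2(1 − ρ)] = (1 + ρ)/2

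| ρ | 1 − ρ² | 60/(1 − ρ²) | (1 + ρ)/2 |
|---|---|---|---|
| 0.3 | 0.91 | 66 | 0.65 |
| 0.5 | 0.75 | 80 | 0.75 |
| 0.7 | 0.51 | 118 | 0.85 |
| 0.8 | 0.36 | 167 | 0.90 |

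The third column is the number of participants an unadjusted 12-week comparison would need to match 60 with adjustment.

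**Simulated omnibus power**, 10,000 replicates per setting, ρ = 0.3/0.5/0.7/0.8:

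| Outcome | Kruskal-Wallis, 12-week | Kruskal-Wallis, change | Rank ANCOVA | Log ANCOVA |
|---|---|---|---|---|
| Log-normal, log-SD 0.8 | 44/45/44/45% | 34/46/68/84% | 48/56/71/85% | 50/59/77/90% |
| Gamma, shape 1.5 | 44/44/44/45% | 35/46/68/85% | 48/56/71/85% | 48/57/73/88% |
| Log-normal, 10% zeros | 44/44/44/45% | 35/46/68/84% | 48/56/71/85% | 31/34/42/49%, log(y + 1) |

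In the first row, the gain of rank ANCOVA, taken before rounding, is 4/11/27/40 points over 12-week values and 14/10/4/2 points over changes. At log-SD 0.5 and ρ = 0.8 the gain over changes is nil (85.1 v 85.2%). The third row matters for IPAQ, whose lowest category, "Physically inactive (<600 MET-min / week", has no lower limit above zero. Adding 1 and taking logs does poorly there.

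A second effect pattern, with one arm shifted by 0.8 SD and 4,000 replicates, gives the same ordering at every ρ of 0.3 or more. At ρ = 0 rank ANCOVA costs essentially nothing against 12-week ranking (69 v 70%).

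**Pairwise power**, arms 0.7 SD apart: Mann-Whitney after a significant Kruskal-Wallis has 43/42/43/43% (12-week) or 32/44/66/83% (change); a Tukey-adjusted rank ANCOVA contrast has 45/53/70/84%.

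**Type I error.** Omnibus: 4.5–5.3% for all four methods. Three Mann-Whitney tests at 0.05 with no gate give at least one false positive in about 12% of null trials, and 4.5–5.1% if gated. Tukey rank contrasts give 4.7–5.2%.

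**Chance imbalance.** In about 25% of null trials some pair of arms differs by at least 0.5 SD at baseline. In these, Kruskal-Wallis on 12-week values rejects in 6/9/13/15%; in the other 75% it rejects in 4/3/2/1%. The average is about 5%. Rank and log ANCOVA stay between 4.4% and 5.7% in both groups.

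**Rule against rule at mild skew** (log-SD 0.3, 5,000 replicates). This compares the SAP's switch with a residual-based switch between ANCOVA and rank ANCOVA:

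- SAP rule: 46/48/55/59% (12-week) or 45/53/73/87% (change)
- Proposed rule: 50/57/74/87%
- Gain: 4/9/19/28 points (12-week) or 5/4/1/0 points (change)

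**How often the switch fires.** A truly normal outcome is sent to the rank branch in about 5% of trials with one pooled test, and in 25–29% with six arm-by-visit tests (1 − 0.95⁶ = 0.265 if independent). With arm-by-visit tests and 12-week values, power is 50/55/70/80%, against 52/59/78/91% under the proposed rule.

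**The case against.** Kruskal-Wallis with Mann-Whitney is a valid, standard route for non-normal data, and no error is shown. That is right, and the claim here is only of lost efficiency and consistency.

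The large gains require 12-week values to be ranked and ρ of about 0.7 or more. Four outcomes are titled as changes, for example "Physical Activity Level Change: Assessed via International Physical Activity Questionnaire-short form (IPAQ"), which favours ranking changes for those four. On that reading the gain is moderate at low correlation and close to nil at 0.8. At log-SD 0.3 and ρ = 0.8 rank ANCOVA even trails slightly as a single test (84 v 86%), although rule against rule the two are equal at 87%. This limits the size of the point but does not reverse it.

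Some further reservations stand in part:

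- Calling the outcomes inconsistently adjusted presumes that baseline is the ANCOVA covariate. That is likely, but the SAP does not say so.
- The Protocol gives no visit times for triglyceride or CRP, and for IPAQ only its title as a change. Baseline for these rests on the SAP's general signed-rank provision.
- The proposed rule keeps a data-driven switch. Its type I error was 4.8–5.9% in the main runs and up to 6.0% in another.
- The 12% familywise figure is a separate multiplicity matter. It supports the Tukey contrasts but is not the core of this point.
- The SAP is written in the past tense. If the analyses have already been run, the change would be post hoc.

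**Conclusion.** The concern holds. For outcomes that fail the normality test, the plan compares programmes with tests that cannot take baseline, although it already needs baseline for the same outcomes. This should be changed as an improvement in efficiency and consistency; it is not a validity failure.

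Under strong skew, 20 per arm and ρ from 0.3 to 0.8, rank ANCOVA gains 4 to 40 points of power over ranking 12-week values and 14 down to 2 points over ranking changes. At mild skew, rule against rule, the ranges are 4 to 28 and 5 down to 0. Correlation, effect size, skew and arm size are all assumed, and it is unknown which outcomes would fail the test. The direction is secure; the size is uncertain.

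**What to change.** Amend the SAP as follows:

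- Name each outcome's own baseline value as the ANCOVA covariate.
- Analyse each continuous outcome by ANCOVA of the 12-week value on arm and baseline, with Tukey-adjusted contrasts of adjusted means and 95% confidence intervals.
- Judge normality once per outcome, on the pooled model residuals (Shapiro-Wilk p < 0.05), not on raw data.
- Pre-specify the log scale only for strictly positive, right-skewed outcomes: triglyceride, and CRP if no value is reported as zero or below detection (its stated reference range starts at 0).
- Where residuals fail, or where zeros are possible (pre-specified for IPAQ), use rank ANCOVA: ranked 12-week value on ranked baseline and arm, with Tukey-adjusted pairwise contrasts. This replaces Kruskal-Wallis and Mann-Whitney. Do not use log(MET + 1) for IPAQ.
- Report medians by arm and visit beside each rank ANCOVA.

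The cost is SAP wording and slightly more analysis work, with no new data. Log-scale effects are read as ratios. Rank ANCOVA gives no estimate in outcome units, hence the medians. The residual check still lets the data choose the scale for some outcomes, but no longer whether baseline is used. If the results have already been analysed, present the new analysis as post hoc.
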